Aim 2: Determine efficacy of initiating the exercise intervention 6 wks post-discharge and compare results with the immediate intervention group by age. Hypothesis 2: The immediate exercise intervention group will improve for all ages at a greater rate and magnitude than the wait-list group for all outcomes.

Aim 3: Determine the immediate exercise intervention's sustainability by analyzing a) rates of extension, adherence, and retention; b) acceptability; and c) efficacy of primary and secondary outcomes. Hypothesis 3: The exercise intervention will be acceptable with >50% extending at wk 6 and >70% adherence and retention at wk 12, with improved primary and secondary outcomes at wk 12.

IMPACT: Our results will provide a novel, practical, portable, low-cost, and enjoyable exercise intervention with important information on its optimal timing and sustainability to fill the gap regarding approaches that are applicable to nearly all post-thoracotomy lung cancer patients for reducing CRF severity and fatigability.^{20,22,27-32}

Section 2.0 Introduction

Significance

2A) OVERALL SCIENTIFIC PREMISE

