use/effectiveness throughout the post-thoracotomy NSCLC population's survivorship trajectory.¹⁰⁴ Sustainability is defined as the continued use beyond the initial implementation of the intervention for the continued achievement of desirable outcomes for the intended population.¹⁰⁴⁻¹⁰⁶ Little research has been conducted with the post-thoracotomy lung cancer population on how to *sustain* changes in exercise behaviors and their associated effects over time for CRF, functional status, and QOL.^{27-29,69} Cochrane reviews²⁷⁻²⁹ state that research is required to investigate how to sustain these positive effects and determine the attributes that lead to success—a key goal of intervention science—to understand if investments are leading to longer-term beneficial outcomes.¹⁰⁴ The design of the proposed exercise intervention combines recommended attributes identified as potential motivators to promote a sustained exercise intervention in the cancer population. These exercise motivators include but are not limited to: use of self-efficacy theory to create intrinsic demand for the intervention;^{29,89} use of a home-based approach³⁰ with service delivery, including face-to-face contact followed up with phone contact;¹⁰⁷ use of informational motivators such as activity logs; portable heart rate monitors and pedometers; and expert consultation provided by qualified health care providers.⁸²

Fig 2: RCT Participant Demographics

Mean age = 67 yrs (range 32-89 yrs)
56% female
74% married
56% retired
29% employed outside home
89% White
7% Black (n = 5)
4% American Indian (n=3)
19% did not complete HS
43% completed HS only
28% some college or post-HS training
10% college and/or post-grad

PRELIMINARY WORK

2N) Two-Arm R21 RCT Pilot Published 2017^{23,24}

Purpose. Examine feasibility, acceptability, and preliminary efficacy of a rehabilitative intervention for CRF severity, fatigability, PSE for fatigue self-management, other symptoms' severity, PSE for walking & balance, and functional performance for post-surgical NSCLC patients.

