Perceived Self-Efficacy	Pain Self-Management	The Perceived Self-Efficacy for Pain Self-Management Inventory (6 Items)	Pre & Post-Surgery Weeks 3, 6, 9, 12	Degree of pain self-management. (0.90)

Aim 2 – Measures – WCG Delayed Intervention. At the start of wk 7, WCG will begin the intervention, concluding at wk 12. Aim 1 study variables and measures (Table 3) will be analyzed for Aim 2 for wks 7-12 to compare with the IIG wks 1-6 outcomes.

Aim 3 – Measures – IIG Intervention Sustainability. At the start of wk 7, IIG participants will be given the option to extend the intervention an additional 6 wks. We will measure the extension rate as % participants who elect to extend. Adherence to the intervention will be measured as % participating in the intervention who adhered to prescribed intervention. Weekly adherence will be calculated by taking number of times prescribed intervention was completed divided by total number of interventions prescribed for week. These data are recorded in the Daily Diary and will be confirmed by research staff reviewing recorded data in Wii Fit-Plus. Retention, measured as part of sustainment, will be calculated as % who elected to extend 6 wks who completed final data collection at wk 12. Based on our conceptual definition of sustainability, we will measure the extent to which components of the intervention were rated acceptable for continued use by participant. Acceptability will be measured at end of wk 6 and 12 using a 15-item Acceptability Questionnaire (Appendix B1) using a numeric scale (1 to 6: 6 = agrees strongly) with higher scores indicating greater acceptability of the exercise program. The Questionnaire has a Flesch-Kinkaid 6th grade reading level and was successfully used in our R21 RCT and allows participants to rate how well barriers and facilitators to exercise are addressed. Open-ended questions provide further input.^{23,24} Efficacy will be measured using the same study variables and measures analyzed in Aim 1 (Table 3) for wks 7-12.

Section 8.0 Drug Formulation and Procurement

Not applicable. This study is not a pharmaceutical trial.

Section 9.0 Toxicity and Adverse Event Reporting Guidelines

Study Monitoring

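### No Hypothesis 3 criterion measures week-12 sustainability on the whole immediate intervention group: retention counts only those who chose to extend, adherence only those participating

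*Combined protocol and SAP*

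**What the plan says.** Hypothesis 3 (Section 1.0) states: "The exercise intervention will be acceptable with >50% extending at wk 6 and >70% adherence and retention at wk 12". It also expects improved outcomes at week 12.

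The Aim 3 measures in Section 7.0 define the three rates:

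- **Extension.** "At the start of wk 7, IIG participants will be given the option to extend the intervention an additional 6 wks", and "We will measure the extension rate as % participants who elect to extend". Whether the denominator is everyone in the IIG or only those reaching the offer is not stated.
- **Retention.** It "will be calculated as % who elected to extend 6 wks who completed final data collection at wk 12". The denominator is explicit: extenders only. The numerator is completed data collection, not exercise.
- **Adherence.** "Adherence to the intervention will be measured as % participating in the intervention who adhered to prescribed intervention". A weekly ratio follows: "number of times prescribed intervention was completed divided by total number of interventions prescribed for week". No level is given at which a participant counts as having adhered.

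Section 2M sets the concept: "Sustainability is defined as the continued use beyond the initial implementation of the intervention", and goes on to tie this to the population for whom the intervention is meant. Section 10.0 makes the week-12 outcome models conditional on having elected to extend. It also describes extension, retention and adherence as binary responses in the IIG at 6 weeks.

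**The concern.** The rates that would carry the sustainability claim are not measured on the arm. Someone who stops in week 3 is outside the retention rate, and so is someone who finishes six weeks and declines more. The week-12 outcome models share this restriction, so they do not bring the whole arm back in.

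The 70% goal also appears in the pilot, on a different base. Section 2N measured pilot retention from the first phone visit after surgery to the final data collection at week 6, and reported 97%. Here the same figure applies to people who have volunteered for six more weeks, so the two rates are not comparable, although readers are likely to compare them.

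At stake is the wording of the Aim 3 conclusion. The trial could report more than 70% retention and adherence at week 12, and describe the programme as sustainable, when a minority of the arm was still in it.

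**Working it through.** **Inputs.** Thresholds of >50% extension, >70% retention and >70% adherence (Hypothesis 3). Attrition of 20%, 90% compliance, 180 evaluable patients and 279 in total (Section 5B). Three arms with equal chance of assignment (Section 4.0).

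**The plan's own figure.** 180/0.8 = 225, and 225/(0.9 x 0.9) = 277.8. Rounded up to a multiple of three this is 279, so 93 per arm. The stated total reproduces. The documents give no combined week-12 sustainability figure to reproduce.

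**Step 1: extension and retention.** These two nest, because the retention denominator is explicit.

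- Share of those offered extension who complete week 12, at the thresholds: 0.50 x 0.70 = 0.35.
- Share of those randomised, assuming all 20% attrition falls before week 7: 0.80 x 0.35 = 0.28.

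**Step 2: adherence, which depends on the reading.**

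- *Headcount among retained extenders (inferred).* 0.50 x 0.70 x 0.70 = 0.245 of those offered. With 20% attrition before the offer, 0.80 x 0.245 = 0.196 of those randomised. Week-6 retention between 97% and 70% gives 0.97 x 0.245 = 0.238 down to 0.70 x 0.245 = 0.171 (rounded down).
- *Headcount among all extenders.* Adherent patients are at least about 0.50 x 0.70 = 0.35 of those offered. Those both retained and adherent lie between 0.50 x (0.70 + 0.70 - 1) = 0.20 and 0.35.
- *Mean session-completion rate.* The number of patients exercising as prescribed cannot be derived from the criterion, so it has no lower bound.

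**Step 3: whole patients.** The thresholds are strict, so the products cannot simply be rounded. With 93 x 0.8 = 74.4, or 74 offered, rounding gives 37, 26 and 18. That sequence fails: 37/74 = 50.0% and 18/26 = 69.2%. The smallest counts that pass on the nested reading are:

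| Stage | Count | Rate | Share of 74 offered | Share of 93 randomised |
|---|---|---|---|---|
| Extend | 38 | 38/74 = 51.4% | 51.4% | 40.9% |
| Retained | 27 | 27/38 = 71.1% | 36.5% | 29.0% |
| Adherent | 19 | 19/27 = 70.4% | 25.7% | 20.4% |

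If all 93 are in the extension denominator, the smallest passing counts are 47, 33 and 24, which is 33/93 = 35.5% retained and 24/93 = 25.8% adherent. With the 60 evaluable patients per arm all offered, they are 31, 22 and 16, and 16/60 = 26.7%.

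**The case against.** The conditioning is open, and those who decline to extend are not hidden: they count directly against the separate >50% extension criterion in the same hypothesis. A careful reader can multiply extension by retention. This stands, but the hypothesis is judged on separate rates, and the product is not among them.

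Only the retention denominator is explicit. If extension is a share of the whole IIG, early dropouts do count against it and the 28% figure no longer applies. Adherence may be a session rate: Section 2N describes the pilot measure in similar terms and reports it as a rate of 93%. A reader might therefore infer that the plan lays down three successively smaller groups, so that a quarter or fewer of the arm satisfies the hypothesis. The documents do not establish that. The figure near a quarter needs the nested headcount reading. Among those offered, the whole-patient examples above give 25.7% to 26.7%, and lower figures need assumed losses before week 7.

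A reader might also infer that thresholds applied to volunteers can hardly fail. No document gives weeks 7-12 data on extenders, and Section 5A notes that adjuvant treatment commonly begins 4-10 weeks after surgery, which can overlap the extension. Failure is possible.

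Extension is optional, so a decliner has no prescription in weeks 7-12 and completed over prescribed is undefined. Scoring such a person as non-adherent would be debatable. This stands and shapes the fix.

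Finally, no test is attached to the thresholds, Section 10.0 only models predictors of the three responses, and the primary Aim 1 analysis is untouched. That limits the consequence to the Aim 3 conclusion.

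**Conclusion.** The concern holds for the denominators. Retention is restricted to extenders, adherence to those participating, and no week-12 criterion uses the whole IIG, which does not fit the plan's own definition of sustainability. The firm figure is that extension and retention can both pass with just over 35% of those offered extension completing week 12. The 28% of those randomised assumes that extension is counted among those offered and that all planned attrition precedes week 7. The figures of about 25% of those offered, and 20.4% of those randomised in the whole-patient example, also rest on the inferred nesting of adherence. If adherence is a mean session rate, no figure can be given.

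The documents also disagree on timing: Hypothesis 3 and Section 7.0 place retention at week 12, while Section 10.0 places all three responses at 6 weeks. The change should be made because the Aim 3 conclusion depends on these definitions. It does not affect the primary analysis.

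**What to change.** In the Aim 3 measures of Section 7.0, base the Hypothesis 3 sustainability conclusion on two shares of all IIG participants allocated to start exercise:

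1. those who extended and completed week 12;
2. those who extended and met a stated per-participant adherence level through week 12.

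Keep non-extenders and dropouts in both denominators as not sustaining the programme, not as non-adherent to a prescription they did not have. State whether adherence is a headcount or a mean session rate, and give the denominator for extension. Keep the retention and adherence rates among extenders, labelled as conditional and shown with their denominators. Reconcile the 6-week timing in Section 10.0 with the week-12 timing in Hypothesis 3 and Section 7.0.

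The extension decision, diary, Wii records and week-12 completion are already to be collected, so no new visit or measure is needed. The cost is wording, one more tabulation and less favourable headline rates.

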5C2) Study Procedures. IIG participants will have baseline data collected by the nurse recruiter. Following principles of transitional care,¹²⁴ the exercise nurse intervener will engage the participant using protocol in Appendix A4 in the hospital post-surgery to review the exercise intervention and teach PSE-enhancing CRF self-management education (Appendix A5) that uses National Comprehensive Cancer Network Guidelines.¹²⁵ To ensure continuity, a primary nurse will be assigned to each participant. Data collectors will contact IIG by phone within approximately 24 hrs of discharge to collect data (if too ill, re-scheduled within approximately 3 days of discharge) and at approximately the end of each week for 6 wks. The nurse will make a phone visit within approximately 24 hrs of post-surgical discharge to screen participant’s readiness to start exercise. Participants will be deemed ready to start if usual level of severity for key symptoms of pain, nausea, and dyspnea are rated ≤ 4 on an 11-point scale (0-10, 10 = most severe). If participant is ready to exercise, a home visit will be scheduled to start exercise within approximately 4 days of discharge. When severity of a key symptom is rated > 4 , nurse will intervene and contact participant’s surgeon’s office for recommendations. The nurse will repeat this step each day until participant is ready to start exercising. Once participant is ready, nurse will arrange home visit within approximately 3 days. The initial home visit will include connecting Wii to participant’s TV, setting up Wii FitPlus log on password, teaching exercise intervention, and reinforcing CRF self-management education and exercise safety precautions. The nurse will follow-up with phone visit within approximately 24 hrs to answer questions and concerns, make a follow-up home visit at approximately the start of wk 2 of exercise, phone visits at approximately the start of wks 3-6, and additional visits per participant request. During visits, nurse will review IIG participant’s Daily Diary (Appendix A2) with participant and provide PSE-enhancing CRF self-management interventions (Appendix A6). These PSE-enhancing interventions include providing mastery and/or vicarious experiences; social encouragement; and reinterpretation of physical and psychological symptoms to support exercise program to adjust exercise prescription per guidelines. Participant uses Daily Diary to record weekly exercise activity and exercise-related symptoms or issues. IIG participants will be given the option to extend exercise for another 6 wks to study wk 12. Data collection will continue on a weekly basis, culminating with a 6MWT at end of approximately wk 12. Nurse calls will continue weekly to prescribe balance exercises and advance walking prescription 5 mins each week, with goal of achieving minimum 30 min/day. Participants may extend beyond 30 min/day with rate of increase no more than 5 min/day each wk, with participants’ PSE for attaining that duration $\geq 70\%$ on a 0-100% scale (100%=high PSE) (Appendix A1).

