
5C2a) WCG participants will have baseline data collected pre-surgery by the nurse recruiter and receive a pedometer and instructions for recording total steps/day in Daily Diary (Appendix A7). The WCG nurse intervener (nurse) will visit in the hospital post-surgery to review study trajectory. Research staff will contact WCG by phone within approximately 24 hrs of discharge to collect post-surgery data (if too ill, data collection rescheduled within 3 days of discharge). Research staff will perform phone visits using protocol in Appendix A8 at the approximate end of wks 1-6 to control for staff interaction and data collection. During wk 6, an exercise nurse intervener will make a phone visit to screen participant’s readiness to start intervention as described for IIG participants. Once participant is ready to start, nurse will arrange home visit within approximately 3 days. The exercise intervention and procedures will be identical to those received by the IIG group during wks 1-6. Staff contact WCG by phone (if too ill, data collection re-scheduled within approximately 3 days) to collect data at the end of approximately wks 7-12.

5C2b) ACG participants will have baseline data collected pre-surgery by a nurse recruiter and receive a pedometer and instructions for recording total steps/day in Daily Diary (Appendix A7). The ACG nurse intervener will visit in the hospital post-surgery to review study trajectory, make a phone visit within approximately 4 days of post-surgical discharge to initiate the ACG intervention (Appendix A3), and make phone visits at the start of approximately wks 2-6. During visits, the nurse will deliver the ACG intervention. Data collectors will contact ACG by phone within approximately 24 hrs of hospital discharge (if too ill, re-scheduled within approximately 3 days of discharge) and at the approximate end of each week for 6 wks to

obtain outcome measures.

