The Principal Investigator of the study will monitor for all potential unanticipated problems that may involve risk to participants and will report adverse events (unanticipated problems), including serious adverse events in accordance to institutional policy. Continuous, close monitoring will occur in several ways. First, adverse events identified during implementation of the intervention are monitored through the nurse who assesses the participant on a weekly basis either by home and/or phone visit utilizing the Daily Diary. The nurse documents any adverse event reported by the participant and immediately reports the occurrence to the Principal Investigator. In addition, the Principal Investigator will monitor participants' Daily Diaries for adverse events and specifically, as it relates to Section 9.0 of this application, any and all adverse events will be reviewed, evaluated, and documented. Using a consultative approach, [name], the Principal Investigator, will ensure reporting of results from the data and safety review to the transdisciplinary team of Co-Investigators and Key Consultants occurring two times a year and more frequently when deemed necessary for the health and safety of participants.

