Note: All 72 two-arm R21 RCT participants used the Daily Diary to record their daily study-related physical activity including number of steps recorded (pedometer).^{23,137-140} used successfully in the R21 RCT without participant complaint about burden. **Note:** In the R21 RCT, no adverse events were reported; participants had a mean age of 67 with a mean of 8 comorbid conditions. The Daily Diary is structured with an area for participants to report experiences related to problems or symptoms during or after exercising. This format of reporting adverse events is supported in the literature and discussed in the Study Protocol in the Research Design Section (Section 5.0) and Study Parameters Section (Section 7.0).¹³⁹ The nurse will review the Daily Diary once a week with the participant and more if necessary to evaluate for potential adverse events. Providing the participant with a means to record problems/symptoms (possible adverse events) will help the participant to develop skills to recognize CRF and other symptoms and effectively develop skills to interpret changes in symptoms and physical functioning.⁶⁷ Likewise, as the participant records the solution to the problems or symptoms (possible adverse events), the participant is building a personal database of health problems and solutions to draw from in the future which enhances their PSE for CRF self-management.⁶⁷ DeNijs and colleagues¹³⁸ reported in a systematic review of the general cancer population that persons with CRF did not adhere to an exercise regimen since they no longer felt certain about their bodies and needed support in order to self-manage fatigue. Thus, the nurse can enhance PSE to self-manage CRF through means of monitoring and interpreting symptoms using the diary to problem solve to make decisions regarding the effect of exercise on CRF and other outcomes. In addition, the Daily Diary outlines the safety procedures for the participant to follow before each exercise session. Moreover, the participant will have phone access seven days a week to contact the nurse should the participant identify or need support in managing problems or symptoms during or after exercising.

Auditing

Auditing is a systematic and independent examination of trial-related activities and documents to determine:

- whether the evaluated trial-related activities were conducted

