- the data were recorded, analyzed, and accurately reported, according to the protocol, to the sponsor's SOPs, GCP, and applicable regulatory requirement(s).

Auditing is a Quality Assurance, one point snapshot of one subject.

This study will undergo audit on at least a quarterly basis by the UNMC Fred & Pamela Buffett Cancer Center Audit Committee.

Detailed policy and procedures for this section may be reviewed at:

<https://www.unmc.edu/cancercenter/clinical/prms.html>

FRED & PAMELA BUFFETT CANCER CENTER DATA AND SAFETY MONITORING COMMITTEE (DSMC) REPORTING

In its initial review, the DSMC will make a recommendation for the frequency of DSMC monitoring based on an assessment of risk associated with study-associated therapy, per the DSMC policy.

All adverse events grade three or higher (expected or unexpected, regardless of attribution) will be reported to the University of Nebraska Medical Center, Fred & Pamela Buffett Cancer Center DSMC in accordance with DSMC guidelines.

An adverse event (AE) is defined as any untoward medical occurrence in a subject or clinical investigation subject participating in a clinical trial, which does not necessarily have a causal relationship with protocol specified therapy. An adverse event can therefore be any unfavorable and unintended sign (including an abnormal laboratory finding), symptom, or disease temporally associated with the use of any investigational therapy/device or intervention, whether or not the event is considered causally related to the use of the product.

Any worsening of a pre-existing condition or illness is considered an adverse event. Laboratory abnormalities and changes in vital signs are considered to be adverse events if they result in discontinuation from the study, necessitate therapeutic medical intervention, meet protocol specific criteria and/or if the investigator considers them to be adverse events. In general, if a laboratory abnormality or change in vital sign is associated with a specific diagnosis that is being reported concurrently as an adverse event the findings that support the diagnosis do not need to be reported as separate adverse events unless the investigator feels it is appropriate.

Treatment-emergent Adverse Event: Treatment-emergent adverse event is defined as any adverse event with onset or worsening from the time of trial intervention until 30 days after the final protocol specified intervention.

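### Adverse-event detection, as described, is tied to the intervention and to exercise and is not matched across arms, and no common comparison window is specified

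*Combined protocol and SAP*

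**What the plan says.** Section 9.0 (Study Monitoring) describes how adverse events come to light:

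- Nurse: "adverse events identified during implementation of the intervention are monitored through the nurse who assesses the participant on a weekly basis", by home or phone visit, using the Daily Diary.
- Diary: the Principal Investigator also reads the diaries, and "any and all adverse events will be reviewed, evaluated, and documented". The diary area meant for this lets participants "report experiences related to problems or symptoms during or after exercising".
- Participant calls: the nurse can be phoned on any day, again about problems linked to exercising.

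The scope set in the same section is wider. An adverse event is any untoward occurrence, causally related or not. Collection runs from signature of the consent form to 30 days after the last protocol intervention, and all events of grade 3 or higher go to the monitoring committee. A treatment-emergent event is "any adverse event with onset or worsening from the time of trial intervention until 30 days after the final protocol specified intervention". Neither the start nor the end of the intervention is defined by arm.

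Sections 5C2, 5C2a and 5C2b give the contacts:

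- IIG: "Participant uses Daily Diary to record weekly exercise activity and exercise-related symptoms or issues", and the nurse reviews it.
- WCG: "Research staff will perform phone visits using protocol in Appendix A8" at about the end of weeks 1–6. An exercise nurse phones in week 6 to screen readiness to start.
- WCG and ACG: participants "receive a pedometer and instructions for recording total steps/day in Daily Diary (Appendix A7"). These subsections describe no other use of that diary.
- ACG: a nurse phones weekly, and the described purpose is to deliver the education.

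Section 10.0 contains no analysis of adverse events.

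**The concern.** The scope is any cause, from consent, in every arm. The described routes are tied to delivery of the intervention or to exercise. Staff who followed the main text alone would look hardest for events in the IIG, less hard in the ACG, and least hard in the WCG during weeks 1–6. Those are the weeks in which the three arms are meant to be compared, in patients who have just had lung surgery and may have complications, as Section 10.0 itself acknowledges.

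The windows add a second imbalance. The treatment-emergent window opens with the intervention, which for the WCG begins at week 7. Follow-up for events closes at different times, and within the IIG the closing date depends on a choice made after randomisation.

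At stake is the reading of the safety data. An excess of events in the IIG could reflect better detection rather than harm, and events in control participants could go unrecorded.

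**Working it through.** The plan gives no adverse-event figure to reproduce. The windows can be rebuilt from its own dates.

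**Inputs**

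- The IIG and ACG interventions start about 4 days after discharge (Sections 5C2, 5C2b): 4/7 = 0.6 weeks.
- The WCG exercises from the start of week 7 to week 12 (Section 7.0, Aim 2): taken as 6.0 to 12 weeks.
- The IIG ends at week 6, or at week 12 if extended (Section 5C2). The ACG ends at week 6 (Section 1.0).
- The tail after the last intervention is 30 days (Section 9.0): 30/7 = 4.3 weeks.

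Study weeks are counted from discharge; a delayed start would shift them.

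**Formulas**

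- Collection ends at last intervention + 30/7: 6 + 4.3 = 10.3, or 12 + 4.3 = 16.3.
- Treatment-emergent window = intervention start to that same end.

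| Group | Treatment-emergent window (weeks after discharge) | Length (weeks) | Part inside weeks 0–6 |
|---|---|---|---|
| IIG, not extended | 0.6 to 10.3 | 9.7 | 5.4 |
| IIG, extended | 0.6 to 16.3 | 15.7 | 5.4 |
| ACG | 0.6 to 10.3 | 9.7 | 5.4 |
| WCG, intervention means exercise | 6.0 to 16.3 | 10.3 | 0 |
| WCG, usual care counted as intervention | 0 to 16.3 | 16.3 | 6.0 |

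Counted from discharge, the later closing date gives 16.3/10.3 = 1.58 times the follow-up. Counted from consent the ratio is smaller, because the same kind of pre-discharge interval is added to both; the documents do not give its length.

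**What unequal detection could do (assumed values)**

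The documents give no detection rates. Suppose the true 6-week risk is 30% in both arms, 90% of events are found in the IIG, and 75%, 60% or 45% are found in a control arm. With 60 per arm (Figure 8) and a two-sided 5% test of two proportions:

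| Control detection | Observed risk, IIG against control | Apparent risk ratio | Chance of nominal significance |
|---|---|---|---|
| 75% | 27% against 22.5% | 1.2 | 0.08 |
| 60% | 27% against 18% | 1.5 | 0.22 |
| 45% | 27% against 13.5% | 2.0 | 0.45 |

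For the middle row, the difference is 0.09. The standard error is √(2 × 0.225 × 0.775/60) = 0.0762 under equality and √((0.27 × 0.73 + 0.18 × 0.82)/60) = 0.0758 otherwise. Then (0.09 − 1.96 × 0.0762)/0.0758 = −0.78, which gives 0.22. With a true risk of 20% the three chances are 0.06, 0.15 and 0.30; with 40% they are 0.10, 0.30 and 0.60. The risk ratio depends only on the two detection rates.

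**The case against.** A reader might infer more than the documents support.

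- *That safety cannot be compared at all.* Collection opens at consent in every arm and overlaps to about week 10.3, so a common window to week 6 already lies inside planned collection. Grade 3 or higher events are reported whatever the arm. A comparison is possible; the difficulty is bias.
- *That WCG events in weeks 1–6 can never be treatment-emergent.* The definition includes worsening, so an early event that worsens after exercise starts does count. The term for the intervention is also undefined for the usual-care period.
- *That the WCG has no nurse contact in weeks 1–6.* There is the week-6 readiness screen, which under the IIG procedure covers pain, nausea and dyspnea.
- *That exercise will look less safe.* This depends on detection rates that nobody has stated.
- *That a planned analysis fails.* Section 10.0 uses neither the treatment-emergent label nor any between-arm table of events.

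Other sources of information also exist. The Principal Investigator reads diaries, and both control arms keep one. The symptom inventory, medications and post-surgical treatments are scheduled weekly in Table 3. The ACG has weekly nurse calls. The WCG call protocol (A8), the control diary (A7) and the ACG script (A3) were not available, and any of them might hold an adverse-event question.

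All of this stands and limits the point. It does not remove it. A scored list of 16 symptoms is not an open question and would not capture a fall, an infection or a readmission. Reporting severe events helps only once they are found. If an appendix does hold a query, Section 9.0 should say so.

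**Conclusion.** The point holds in a limited form. As the main text stands, detection of adverse events is not described as equal across arms, and the WCG in weeks 1–6 is the least well covered. Closing dates differ by about 6 weeks (10.3 against 16.3). If the trial intervention means exercise, a WCG event with onset in weeks 1–6 is treatment-emergent only if it worsens later. Any between-arm safety comparison would carry both biases. The direction and size of the detection bias are unknown; the risk ratios above are illustrations under assumed rates. The conclusion rests on the main text only and would narrow if A3, A7 or A8 contained a uniform query. It is an improvement that should be made, at low cost; the primary efficacy analysis is not affected.

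**What to change.** 1. Add one identical open adverse-event question to the weekly data-collection call already made to all three arms in weeks 1–6, asked by the same type of staff, and name it in Section 9.0.
2. Add to Section 10.0 a between-arm table restricted to events found through that shared question, over one common window ending at week 6. The restriction matters: otherwise the IIG keeps its nurse and diary review as an extra source.
3. List separately the events found only through nurse or diary review, events before the window opens, and later events by weeks on exercise.
4. Define by arm when the trial intervention starts and ends. Section 5C1a has the IIG exercising through weeks 1–12, while Sections 5C2 and 7.0 (Aim 3) make weeks 7–12 optional. These passages must be reconciled, because they set the IIG closing date.

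The cost is one question per existing call and a table definition. The downside is that more control-arm events will be recorded. If the calls are already complete, a common-window table can still be built from onset dates, with the unequal ascertainment disclosed.
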